12.0 CRITERIA FOR REMOVAL FROM STUDY

- **12.1. Disease Progression:** Patients with confirmed progressive disease following POLAR treatment will be removed from treatment, their disease pathologically documented, and the patient will be followed for survival and the immunologic endpoints. However, in the absence of unacceptable toxicity, participants who meet criteria for disease progression per RECIST 1.1 while receiving treatment will be permitted to continue treatment if in the opinion of the treating MD the patient is continuing to derive benefit from the treatment. iRECIST will be used to evaluate the response and the co-primary endpoint of overall response rate will be assessed both by RECIST and iRECIST.
- **12.2 Extraordinary Medical Circumstances:** If at any time the constraints of this protocol are detrimental to the patient's health, the patient shall be withdrawn from treatment. In this event:
 - 12.2.1. Document reasons for withdrawal and record whether this action was patient or physician directed.
 - 12.2.2. The patient will remain technically on-study although treatment has been discontinued. The patients will be followed for relapse and survival.

12.3. Unexpected or Life-Threatening Toxicity (CTCAE v5.0 Table):

- 12.3.1. Direct questions regarding drug therapy to the Principal Investigator.
- 12.3.2. Reporting requirements and procedures depend upon:
 - (1) whether agents are suspected of causing toxicity, (2) whether possibility of such toxicity was reported in the consent form, or manufacturer's literature (Published Toxicity), (3) the severity or grade of the toxicity.
- 12.3.3. Expected toxicities:
- 12.3.3.1. Grade 4 myelosuppression: Report only as part of regular data submission.
- 12.3.3.2. All other toxicities, Grades 4: Written Report to Principal and Co-Investigators, within 10 working days.
- 12.3.3.3. All other toxicities, Grades 1 to 3: Report only as part of regular data submission.
- 12.3.4. Unexpected Toxicities: Unexpected toxicities are toxicities that are not listed in the toxicity management section of the protocol, the consent form, or the manufacturer's package inserts. All unexpected toxicities will be reported to Principal and Co-Investigators, within 10 working days.
- 12.4. Patient noncompliance with the protocol requirements
- 12.5. Patient request to withdraw
- 12.6. Development of serious intercurrent illness during treatment
- 12.7. Patient removed at the discretion of the PI

13.0 CRITERIA FOR OUTCOME ASSESSMENT AND ENDPOINT EVALUABILITY

13.1. Tumor Measurements

Response Evaluation Criteria in Solid Tumors (RECIST) version 1.1 will be used to determine treatment response. Baseline tumor measurements will be performed prior to initiation of therapy. These measurements should be done according to iRECIST (see Appendix 2) ⁵⁴. An estimate of overall objective and subjective response will be made and recorded at the end of treatment at 8 weeks after the last infusion. Since it is expected that immune activity would lead to tumor flare, the restaging CT scans may be repeated 8 weeks later based on irRECIST and the designation of iCR, iPR, iSD, iUPD, or iCPD will be made at that time. Best overall response will be used.

- **13.1.2.** Disease control rate (DCR): DCR is defined as the percentage of patients who have achieved complete response, partial response, and stable disease to the study treatment.
- **13.1.3.** Overall response rate (ORR): ORR is defined as the percentage of patients who have achieved complete response and partial response to the study treatment.
- **13.1.4. Best Overall Response (BOR):** BOR is defined as the best response recorded from the start of the study treatment until the disease progression/recurrence.
- **13.1.5.** Durable response rate (DRR): DRR is defined as the percentage of patients who had achieved continued disease responses (CR and PR) for more than 6 months.
- **13.1.6.** Durable disease control rate (DDCR): DDCR is defined as the percentage of patients who had achieved continued disease controls (CR, PR, and SD) for more than 6 months from the time from the initiation of study treatment.
- **13.1.7. Additional Assessments.** All patients will have a baseline tumor marker assessment and testing of tumor markers at the designated follow-up time points. Changes in serial tumor marker measurements, in those patients who have baseline elevations, will be utilized as a surrogate marker of clinical response, stable disease or disease progression and reported as such.
- **13.1.8. Patients without residual disease:** For patients whose primary tumor or metastatic disease has been removed or successfully treated, respectively, prior to entry into this trial, progression free survival will be evaluated based on duration of relapse-free survival.
- **13.1.9. Progression free survival (PFS):** PFS is defined as the time from the initiation of study treatment to radiographic progression or death.
- **13.1.10. Overall survival (OS):** OS is defined as the time from the initiation of study treatment to the date of death from any cause.

13.2 Criteria for Study Endpoint Evaluability

- All patients who receive at least one dose of olaparib and pembrolizumab are considered to be evaluable for toxicity.
- All patients who receive at least olaparib for 14 days of 21-day course and one dose of pembrolizumab are considered to be evaluable for efficacy evaluation.

- Patients who enroll with a complete response on platinum-based treatment are evaluable and a radiographical disease recurrence by RECIST v 1.1 will be considered a progression.
- Patients who are screened eligible but subsequently withdraw from the study prior to receiving pembrolizumab with olaparib are considered inevaluable and will be replaced on the study.

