10.2 Timing of Dose Administration

Trial treatment should be administered on Day 1 of each cycle after all procedures or assessments have been completed as detailed on the Trial Flow Chart (Section 6.0). Trial treatment may be administered up to 3 days before or after the scheduled Day 1 of each cycle due to administrative reasons. On the day of the treatment, participants can receive oral olaparib AM dose at the clinic visit followed by pembrolizumab.

All trial treatments will be administered on an outpatient basis.

Pembrolizumab will be infused per MSK guidelines. Pembrolizumab 200 mg will be administered as a 30-minute IV infusion every 3 week. After the first 6 months (9 cycles), on C10D1 Pembrolizumab 400 mg IV every 6 week plus olaparib 300 mg twice a day orally will be continued. Pembrolizumab 200 mg IV every 3 weeks may continue after Cycle 9, and Pembrolizumab 400 mg IV every 6 weeks may begin earlier than Cycle 9 per treating physician's discretion. Given the variability of infusion pumps a window of -5 minutes and +10 minutes is permitted (i.e., infusion time is 30 minutes: -5 min/+10 min).

8

POLAR: a phase 2 trial for pembrolizumab and olaparib maintenance for metastatic PDAC and HRD and/or Exceptional Response to Platinum – Ver. 5/3/2020

10.3 Dose Modification and Toxicity Management for Immune-Related AEs Associated with Pembrolizumab

AEs associated with pembrolizumab exposure may represent an immunologic etiology. These immune-related AEs (irAEs) may occur shortly after the first dose or several months after the last dose of pembrolizumab treatment and may affect more than on body system simultaneously. Therefore, early recognition and initiation of treatment is critical to reduce complications. Based on existing clinical study data, most irAEs were reversible and could be managed with interruptions of pembrolizumab, administration of corticosteroids and/or other supportive care. For suspected irAEs, ensure adequate evaluation to confirm etiology or exclude other causes. Additional procedures or tests such as bronchoscopy, endoscopy, skin biopsy may be included as part of the evaluation. Based on the severity of irAEs, withhold or permanently discontinue pembrolizumab and administer corticosteroids. Dose modification and toxicity management guidelines for irAEs associated with pembrolizumab are provided in Table 3.

Table 3 Dose modification and toxicity management guidelines for immune-related AEs associated with pembrolizumab

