14.1 Populations for Analyses

• Safety Analysis Dataset: Safety analyses will be conducted for all evaluable participants who took at least one dose of study intervention.

• **Primary Efficacy Dataset**: participants who receive at least olaparib for 14 days of 21-day course and one dose of pembrolizumab are considered to be evaluable for efficacy evaluation.

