If a patient requires discontinuation of either olaparib or pembrolizumab for reasons of toxicity and if in the opinion of the treating MD the patient is continuing to derive benefit, the patient is able to continue on study.

- All AEs from the time of treatment allocation/randomization through 30 days following cessation of study treatment must be reported by the investigator.
- All AEs meeting serious criteria, from the time of treatment allocation/randomization through 90
 days following cessation of study treatment, or 30 days following cessation of study treatment if the
 participant initiates new anticancer therapy, whichever is earlier must be reported by the investigator.
- All pregnancies and exposure during breastfeeding, from the time of treatment allocation/randomization through 120 days following cessation of study treatment, or 30 days

following cessation of study treatment if the participant initiates new anticancer therapy must be reported by the investigator.

 Additionally, any SAE brought to the attention of an investigator at any time outside of the time period specified above must be reported immediately by the investigator if the event is considered to be drug-related.

Investigators are not obligated to actively seek AE or SAE or other reportable safety events in former study participants. However, if the investigator learns of any SAE, including a death, at any time after a participant has been discharged from the study, and he/she considers the event to be reasonably related to the study treatment or study participation, the investigator must promptly notify Merck.

Possible Side Effects of pembrolizumab

COMMON, SOME MAY BE SERIOUS

In 100 people receiving pembrolizumab more than 20 and up to 100 may have:

- Itching of the skin
- Loose or watery stools
- Cough

OCCASIONAL, SOME MAY BE SERIOUS

In 100 people receiving pembrolizumab from 4 to 20 may have:

- Joint pain
- Rash
- Fever
- Back pain
- Pain in the belly
- Loss of skin color
- Not enough thyroid hormone (hypothyroidism), which may make you feel tired, gain weight, feel cold, or have infrequent or hard stools
- Low levels of salt in the blood (hyponatremia), which may make you feel tired, feel confused, have a headache, have muscle cramps, and/or feel sick to your stomach
- Inflammation of the lungs (pneumonitis), which may make you feel short of breath and cough

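### Sections 13.2 and 14.1 of the protocol define the safety population differently, and on one reading a patient exposed to only one drug is left out of the safety tables

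*Protocol*

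**What the plan says.** The protocol defines who counts for safety in two places.

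- **Section 13.2, toxicity:** "All patients who receive at least one dose of olaparib and pembrolizumab are considered to be evaluable for toxicity".
- **Section 13.2, replacement:** patients screened as eligible who then "withdraw from the study prior to receiving pembrolizumab with olaparib are considered inevaluable and will be replaced on the study". No exception is made for someone who has already taken one of the drugs.
- **Section 14.1, Safety Analysis Dataset:** "Safety analyses will be conducted for all evaluable participants who took at least one dose of study intervention".

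Three other places bear on the point. Section 10.2 describes the order of dosing: "On the day of the treatment, participants can receive oral olaparib AM dose at the clinic visit followed by pembrolizumab". Section 15.0 sets the reporting duty: "All AEs from the time of treatment allocation/randomization through 30 days following cessation of study treatment must be reported by the investigator". Section 2.0 makes safety a secondary objective, and Section 14.0 has adverse events described and tabulated by cohort, with no test or threshold attached.

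**The concern.** A safety population normally contains everyone exposed to any study drug. Here the toxicity definition in 13.2 asks for exposure to both. Section 14.1 looks broader, but it limits its set to *evaluable* participants, and 13.2 is the only place where evaluability for toxicity is defined.

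A patient who leaves after one drug may have left because of an early adverse event. An exclusion triggered by early departure can therefore be related to the outcome that the safety objective is meant to describe. The cohorts are small (33, 15 and 15), so one patient more or less is visible in a table. It should also be clear from the protocol which denominator every adverse event percentage uses.

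**Working it through.** **Step 1. What does 13.2 require?** The toxicity definition joins the two drugs with *and*. The replacement rule, which turns on receiving pembrolizumab with olaparib, supports the reading that both are needed.

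**Step 2. What does 14.1 require?** The dose condition alone is met by either drug. The result therefore turns on *evaluable*, and there are two alternatives:

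| Reading of *evaluable* in 14.1 | One-drug patient in safety dataset? | Consequence |
|---|---|---|
| Carries the 13.2 toxicity meaning | No | 13.2 and 14.1 agree, but an exposed patient is missing from the tables |
| Does not carry it | Yes | 13.2 and 14.1 define different sets with different denominators |

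Only one of these can hold at a time. Each leaves a defect, and the protocol does not say which is meant.

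**Step 3. Can one-drug exposure occur?** Yes. Section 10.2 lets olaparib be taken at the visit before the infusion, so a patient could take olaparib, have an event and never receive pembrolizumab.

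**Step 4. When is such a patient replaced?** Only on withdrawal from the study. A one-drug patient who stays on study is not covered by the replacement rule, and only the exclusion from the safety set is in question.

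**Step 5. Size.** The protocol states no figure for this, so there is none to reproduce. The inputs are the planned numbers in Section 1.0: 63 in total, with 33 in Cohort A and 15 each in Cohorts B and C. Suppose k patients receive one drug, have a given event, withdraw and are replaced, and nobody else has that event. With N planned patients:

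- both-drugs set: 0/N
- all exposed patients: k/(N + k)

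The protocol gives no value for k, so k = 1 to 3 is an assumption.

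| | Both-drugs set | k = 1 | k = 2 | k = 3 |
|---|---|---|---|---|
| All cohorts (N = 63) | 0/63 | 1/64 = 1.6% | 2/65 = 3.1% | 3/66 = 4.5% |
| Cohort A (N = 33) | 0/33 | 1/34 = 2.9% | 2/35 = 5.7% | 3/36 = 8.3% |
| Cohort B or C (N = 15) | 0/15 | 1/16 = 6.3% | 2/17 = 11.8% | 3/18 = 16.7% |

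Each row for a single cohort assumes that all k patients belong to that cohort.

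**Step 6. Does anything else depend on it?** No. The Cohort A stopping rules, error rates and power concern response and 6-month PFS and do not use the safety set.

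**The case against.** The case for leaving this alone has several parts, most of which limit the point without removing it.

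- **Section 14.1 is the section on analysis populations, and its dose condition is already the usual one.** This is fair, and it is why exclusion cannot be asserted as settled. But the section restricts itself to *evaluable* participants, and the only toxicity meaning of that word is the two-drug one. If 14.1 is meant to be broader, it contradicts 13.2.
- **A reader might infer that every patient harmed after one drug is dropped and replaced.** The text does not support that. Exclusion follows on only one of the two readings. Replacement requires withdrawal from the study, and the rule's natural target is withdrawal between screening and treatment. Sections 10.1 and 15.0 let a patient who stops one drug for toxicity continue on study if judged to be benefiting, and Section 12.2 keeps patients withdrawn from treatment for extraordinary medical circumstances on study.
- **A reader might infer that the exclusion always flatters the safety profile.** It does not. It lowers the rate only of events that the excluded patient had. Without replacement it raises the rate of all others: three events in 15 patients (20.0%) become three in 14 (21.4%) if the patient left out did not have that event.
- **A reader might infer that the events are lost.** They are not. The reporting duties in Sections 15.0 and 15.1 do not depend on receiving both drugs. The loss, if any, is from the summary tables and denominators.
- **The situation is rare.** Probably so. The route through Section 10.2 is an event between the first tablet and the infusion on the same visit.

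**Conclusion.** The point holds as a defect of wording with a limited effect. Sections 13.2 and 14.1 either leave an exposed one-drug patient out of the safety tables or define two different safety populations, and the protocol does not settle which. This is not detail that could be left to a statistical analysis plan, because the protocol itself states the population twice and the statements do not match.

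The effect is confined to descriptive tables for a secondary objective. For one replaced patient with an otherwise unseen event it is 1.6 percentage points overall, 2.9 in Cohort A and 6.3 in Cohort B or C. These figures assume that *evaluable* carries the 13.2 meaning and that the patient withdrew and was replaced. That few patients will be affected is a judgement from both drugs being started together; the protocol gives no expected number. The efficacy design is untouched.

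**What to change.** 1. In both 13.2 and 14.1, define the safety set as every participant who received one or more doses of olaparib or of pembrolizumab.
2. Delete *evaluable* from the safety definition in 14.1.
3. State in 13.2 that a replaced patient who received either drug stays in the safety tables, and that replacement affects only the efficacy count.

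The cost is a few lines of wording. Sample size, stopping rules, the efficacy set and treatment all stay as they are. If one-drug patients are replaced, the safety denominator may exceed the planned 63, and the tables should show the actual number exposed.

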14.0 BIOSTATISTICS

This is a phase 2, open-label, non-randomized study evaluating the novel combination of pembrolizumab and olaparib (POLAR) in three cohorts of metastatic PDAC s with homologous recombination deficiency (HRD) in the first-line or second-line on-platinum maintenance setting, two of which are genomically enriched and one is identified by platinum sensitivity. The primary objective of the study is to determine both the 6-month PFS rate by RECIST v1.1 as well as the objective response rate (ORR, CR+PR) by iRECIST for this combination. Both factors will be considered for purposes of sample size determination as follows and a two-stage design will be employed. The secondary endpoints of this study are overall survival (OS), progression-free survival (PFS) by both RECIST v1.1 and iRECIST, disease control rate (DCR) by both RECIST v1.1 and iRECIST, CA 19-9, and CEA response. Progression-free survival (PFS) will be analyzed from both the consent date and treatment start date (C1D1), separately, due to the maintenance trial design. Exploratory scientific correlates include assessments of HRD genetic mutational signatures, neoantigens, immunogenic tumor microenvironment, clonal evolutionary dynamics to study heterogeneity, andresistance mechanism to POLAR. Exploratory endpoints will also include second progressionfree survival (PFS2) from time of subsequent systemic treatment start post-POLAR to progression on that treatment as well as assess duration of the first-line or second-line treatment prior to POLAR treatment. Exploratory endpoints will also assess genetic signatures and compare clinical outcomes, evaluate reversion mutation, zygosity, plasticity and aneuploidy from tumor and ctDNA, and to assess the role of maintenance treatment with minimally residual disease by the presence of ctDNA and CA 19-9 and its trend prior to treatment.

A two stage design will be employed only in Cohort A with co-primary endpoints ORR by iRECIST and 6-month PFS rate⁷ by RECIST v1.1. An initial cohort of 20 patients will be treated. If 14 or more patients are alive and progression free at the 6 months follow-up or if 6 or more objective responses are observed, an additional 13 patients will be accrued for a total of 33 patients. If 23 or more of the 33 patients are alive and progression free at 6 months from start of treatment or if 12 or more objective responses are observed, we can conclude that the regimen is sufficiently active to warrant further testing in this group of patients. We will also evaluate the progression-free survival from the consent date secondarily to the treatment start date (C1D1). We used the reference from historical data for these co-primary endpoints. 6-months PFS rate was 50% and ORR was 20% in singleagent olaparib study arm compared to placebo control arm in maintenance setting⁷. This design yields 81% power to detect a true 6-month PFS rate of 77% or more and it yields 81% power to detect a true ORR of at least 43%. It yields approximately 0.95 probability of a negative result if the true 6-month PFS rate is no more than 53% and the true ORR is no more than 20%. The type I error for the ORR endpoint is 0.02 and the type I error for the PFS endpoint is 0.028 and so the overall type I error of the composite design is bounded at 0.05 (the sum of the two type I error rates for PFS and RR) while the type II error rate for the composite design is 0.09 (each design has a type II error rate of 0.09). The probability of early termination was calculated as the product of the probability of early termination for the PFS endpoint (0.904) and the probability of early termination for the RR endpoint (0.804), resulting in a probability of early termination of 0.73 for the composite endpoint. These calculations assume that ORR and PFS are independent, , the type 1 error slightly decreases if ORR and PFS are positively correlated, which is very likely. The calculations also assume that the 6 month PFS endpoint is binary. Patients who are lost to follow up before their 6 months PFS

evaluation and who did not respond or do not have documented response before their being lost to follow up will be counted as events (nonresponders/progressors) for the composite primary endpoint. However this will be uncommon. If after the first stage we meet the rule of observing 6 or more responses out of the 20 patients enrolled in the first stage, then no waiting is required and we can proceed with enrollment to the second stage. However, if we do not observe 6 out of 20 responses after the first stage, we will halt accrual after the first 20 patients until we obtain the 6-month PFS status for these 20 patients. The interim look for Cohort A will not affect accrual to Cohorts B and C.

Cohorts B and C will be exploratory and will enroll 15 patients each. ORR will be estimated using the binomial distribution along with exact 95% confidence intervals. With 15 accrued patients, we can estimate the DCR to within +/- 25% margins of error with 95% confidence.

Secondary objectives

Adverse events will be summarized descriptively and tabulated separately for each cohort. DCR will be estimated using binomial proportions along with exact 95% confidence intervals while PFS and OS will be estimated using the Kaplan-Meier method separately for each of the 3 cohorts. CEA and CA 19-9 will be summarized using medians and interquartile range.

Exploratory objectives

Wilcoxon rank sum test will be used to assess associations between genetic and transcriptomic signatures at baseline with response while Cox regression will be used to assess associations with PFS and OS. These analyses will be conducted separately for each cohort acknowledging the exploratory nature of these analyses particularly for Cohorts B and C which have limited sample size. Changes between baseline and after treatment in neoantigen induction, TME, and immunomodulatory targets will be summarized descriptively using medians and interquartile range for each cohort separately. To understand the resistance mechanisms, post-treatment changes (4-6 weeks and at progression) of tumor samples and circulating tumor DNA (MSK-ACCESS) from baseline will be associated with response using Wilcoxon rank sum test while Cox regression will be used for PFS and OS outcomes. Finally, in selected patients with viable organoids available from IRB# 15-149 prior to enrollment to POLAR trial, we will concurrently evaluate the response of organoid to POLAR in real time as participants are treated in parallel. Dr. [name] will oversee this part. PFS2 will be estimated using the Kaplan-Meier method. Associations between genetic mutations (HRD and non-HRD) and outcome will be assessed using Fisher's exact test for response and log-rank test for survival outcomes. Biomarkers (reversion mutation, zygosity, plasticity, aneuploidy from tumor, and circulating tumor DNA) will be summarized using proportions. Presence of circulating tumor DNA and levels of CA 19-9 prior to treatment at time points prior to consent and between the consent and start date will be graphically summarized at each timepoint.

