7.0 RECRUITMENT PLAN

All participants meeting the eligibility requirements will be considered for enrollment regardless of sex, race, or religion. Subjects will be accrued from the Solid Tumor Gastrointestinal Oncology Service (STGI). Eligibility criteria may not be waived by the investigator. Discussions regarding protocol enrollment and participant eligibility will begin with any of the investigators named on the consenting professionals list. Participants will be made aware of the protocol, its specific aims and objectives, and the potential risks and benefits the subjects may incur. Participants will be required to read, agree to, and sign an institutional review board (IRB)-approved informed consent form prior to registration for this trial. Participants will be consented prior to screening activities and treatment initiation. Our target accrual is minimum 47 (Cohort A: 18, B: 15, C: 15) to maximum 63 eligible patients. Approximately 800 patients with PDAC are seen at MSK annaully. About 125 patients have HRD who are expected to meet the genetic eligibility criteria for Cohort A and B and about 50-75 for Cohort C each year. Based on our experience with previous trials of this type, we expect an accrual time of approximately 2.5-3 years.

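### Two stated design figures are wrong: a type II error of 0.09 per endpoint beside 81% power (the rules give 0.19), and a minimum accrual of 47 with 18 in Cohort A (the design gives 50 with 20)

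*Protocol*

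**What the plan says.** Section 14.0 sets a two-stage design for Cohort A. On stage 1 it says "An initial cohort of 20 patients will be treated". The trial continues on either endpoint: "If 14 or more patients are alive and progression free at the 6 months follow-up or if 6 or more objective responses are observed", then "an additional 13 patients will be accrued for a total of 33 patients". The final rule is again either/or. For PFS it reads "If 23 or more of the 33 patients are alive and progression free at 6 months from start of treatment"; for ORR the cut-off is 12 responses of 33.

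On power the section says "This design yields 81% power to detect a true 6-month PFS rate of 77% or more and it yields 81% power" for a true ORR of at least 43%. A few lines later, on type II error, it says "while the type II error rate for the composite design is 0.09 (each design has a type II error rate of 0.09". It also says that its calculations take ORR and PFS as independent.

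Section 7.0 says "Our target accrual is minimum 47 (Cohort A: 18, B: 15, C: 15) to maximum 63 eligible patients". Section 14.0 adds that, if the stage 1 response rule is not met, accrual to Cohort A pauses after 20 patients, and that this interim look leaves Cohorts B and C (15 patients each) untouched.

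**The concern.** Type II error is one minus power at the same alternative. A per-endpoint power of 81% and a per-endpoint type II error of 0.09 cannot both be true. Nor can an either/or rule on two independent endpoints have the same type II error as each endpoint alone when both alternatives hold, because a miss then requires both to fail.

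The sentence states the error rates of the only powered analysis in the trial. A reader who takes 0.09 as the per-endpoint figure would halve the chance of missing a real effect on that endpoint. A reader who takes 0.09 as the composite figure would be misled in a direction that depends on which alternatives hold.

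The minimum accrual in Section 7.0 conflicts with the stage 1 size in Section 14.0 and with its own addends.

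**Working it through.** **Inputs (protocol, Section 14.0).** Stage 1 n1 = 20, total n = 33, stage 2 n2 = 13. PFS cut-offs 14/20 and 23/33; ORR cut-offs 6/20 and 12/33. Null rates 53% (PFS) and 20% (ORR); alternatives 77% and 43%.

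**Per-endpoint formula.** With X1 ~ Bin(20, p) and X2 ~ Bin(13, p):

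P(success | p) = Σ over x ≥ r1 of P(X1 = x) · P(X2 ≥ r − x)

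**Reproducing the plan's other figures.**

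| Quantity | Stated | Computed |
|---|---|---|
| Power, PFS at 77% | 81% | 0.806 |
| Power, ORR at 43% | 81% | 0.809 |
| Type I error, PFS at 53% | 0.028 | 0.0281 |
| Type I error, ORR at 20% | 0.02 | 0.0201 |
| Early termination, PFS, P(X1 ≤ 13) | 0.904 | 0.904 |
| Early termination, ORR, P(X1 ≤ 5) | 0.804 | 0.804 |
| Early termination, both | 0.73 | 0.904 × 0.804 = 0.727 |
| Either/or type I error, independent | at most 0.05 | 0.0496 |

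All of these agree, so the rules have been read as the protocol intends.

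**Type II error per endpoint.**
- PFS: 1 − 0.806 = 0.194. Of this, 0.156 comes from missing 14/20 and 0.038 from missing 23/33 after passing stage 1.
- ORR: 1 − 0.809 = 0.191. Of this, 0.078 comes from missing 6/20 and 0.112 from missing 12/33 after passing stage 1 (parts rounded).

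Dropping the interim look does not give 0.09 either: the type II errors would be 1 − 0.883 = 0.117 (PFS) and 1 − 0.828 = 0.172 (ORR).

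**Type II error of the either/or rule.** Enumerate the joint outcome, continue if either stage 1 cut-off is met, and succeed if either final cut-off is met. Two cases are shown: independent endpoints (the protocol's assumption) and fully nested endpoints, where every responder is also progression-free at 6 months. Nesting is the strongest positive association these rates allow.

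| True rates (PFS / ORR) | Independent | Nested |
|---|---|---|
| 77% / 43% (both alternatives) | 0.028 | 0.069 |
| 77% / 20% (PFS only) | 0.177 | 0.187 |
| 53% / 43% (ORR only) | 0.183 | 0.191 |

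The first entry lies below the simple product 0.194 × 0.191 = 0.037 because passing stage 1 on one endpoint keeps the other in play. None of the six values is 0.09.

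**Minimum accrual.** The parts in Section 7.0 give 18 + 15 + 15 = 48, not 47. With the stage 1 size from Section 14.0, the minimum is 20 + 15 + 15 = 50. The stated maximum is right: 33 + 15 + 15 = 63, as in the protocol summary (Section 1.0).

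**The case against.** The strongest reply is that nothing operational depends on either figure. The correct 81% power stands a few lines above the 0.09, so a careful reader can recover 0.19. The decision rule is either/or, so a negative Cohort A means that both endpoints failed; with both alternatives true that probability is 0.028 to 0.069, below the printed 0.09. All of this stands. It limits the consequence but does not make the sentence right: 0.09 for each endpoint is contradicted by the paragraph itself, and the composite figure is too low when only one endpoint improves.

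Three stronger readings are tempting, and the protocol does not support them.
- A reader might infer that Cohort A could stop at 18 and leave the 14/20 and 6/20 rules unusable. Section 14.0 does not allow this: it treats 20 patients before the rule is applied. Section 7.0 is an accrual forecast, not a stopping rule.
- A reader might infer that the design is underpowered relative to its claim. It is not, because the claimed 81% reproduces for both endpoints.
- A reader might count the Cohort B and C precision statement as a third error: "With 15 accrued patients, we can estimate the DCR to within +/- 25% margins of error with 95% confidence". This is the usual worst-case normal-approximation half-width, 1.96 × √(0.25/15) = 25.3 points. The planned exact interval has a half-width above 25 points only for 6 to 9 events of 15, with a peak of 26.1. One exact limit can lie 28.4 points from the estimate (4 or 11 events), but the half-width there is 23.7 points. DCR is a listed secondary endpoint, and the margin at n = 15 is the same whichever proportion is named.

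**Conclusion.** Two stated figures are wrong. The type II error is 0.19 per endpoint, about twice the printed 0.09. The composite value depends on the scenario: about 0.03 under independence and up to about 0.07 under full nesting when both alternatives hold, and 0.18 to 0.19 when only one holds. Correcting the text therefore makes the per-endpoint figure less favourable and, when both alternatives hold, the composite figure more favourable. Minimum accrual is understated by 3 (47 against 50), and Cohort A's share by 2 (18 against 20).

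The per-endpoint results rest only on the protocol's cut-offs and alternative rates and on binary 6-month PFS, as the protocol assumes. The composite results also rest on reading both rules as either/or at each stage and on the stated association between endpoints. These are errors of reporting. They are worth correcting because they describe the primary design, but they do not call the sample size, the cut-offs or the type I error into question.

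**What to change.** In Section 14.0, replace the type II statement with wording such as: each endpoint has a type II error of 0.19; the either/or rule has a type II error of about 0.03 under independence (up to about 0.07 if every responder is also progression-free at 6 months) when both alternatives hold, and about 0.18 to 0.19 when only one holds.

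In Section 7.0, replace the lower bound with: minimum 50 (Cohort A: 20, B: 15, C: 15). Leave the maximum of 63 as it is.

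The cost is two sentences. No cut-off, sample size or analysis changes, and the Cohort B and C precision sentence can stay.
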